2.5 Definition of Study Dates and Observation Period End Dates	Up-to-Day 180 observation period end date for subjects who withdrew early is maximum of withdrawal date and randomization date+180 days.
2.6 Subgroups	Subgroup criteria for the Khorana score is update to 2, 3, 4, and ≥ 5 .
4.3 Treatment Compliance	Treatment compliance definition is updated. This is based on exposure data for subjects and based on the duration the subjects were in the trial.
4.5 Systemic Cancer Therapies and Concomitant Medications	Systemic cancer therapies taken at randomization and during the double-blind period as well as concomitant medications taken during double-blind period is defined.
5.2.4 Subgroup Analysis for Primary Efficacy Composite Endpoint	Subgroup analysis will be performed if there are at least 30 total randomized subjects in each subgroup category
5.6, 5.6.1 Additional Secondary Efficacy Variables Definition	A 3 rd composite endpoint is added to the secondary efficacy endpoints. This is a composite of events in the primary efficacy composite endpoint, fatal/non-fatal ATE, and visceral VTE. A 4 th composite endpoint is added to the secondary efficacy endpoints. This is a composite of symptomatic VTE events and major bleeding
9 Health Care Resource Utilization	Section heading relabeled and only descriptive statistics (frequency counts, mean, median, SD) will be presented.
Attachment	Added IDMC Data Preparation Specification.
Version 3.0 to 4.0	Document resaved with no changes made to v3.0
Changes from v2.0 to 3.0	
1.0 Introduction	Updated the version of the protocol to Amendment INT-4 finalized on February 16, 2018.
1.1 Study Objectives/Primary Objective	The occurrence of symptomatic lower extremity distal DVT event is included in the primary objective based on the amended protocol (v4.0).
1.3 Statistical Hypothesis for Study Objective	The occurrence of symptomatic lower extremity distal DVT event is included in the composite.
1.4 Sample Size Justification	Section updated based on the amended protocol (v 4.0). The following text is added – Towards the end of the enrollment phase, approximately 800 subjects were planned to be randomized into the study due to the high subject discontinuation rate.
2.4 Definition of End-of-Study date	The End-of-Study date updated to include the last assessment date during the study, including the Day 210/Post-Treatment Follow-Up visit.
5.2 Primary Efficacy Composite Endpoint 5.2.1 Definition	The occurrence of symptomatic lower extremity distal DVT event is included in the primary efficacy composite endpoint.

5.2.4 Subgroup Analyses for the Primary Endpoint	Subgroup analysis will be performed if there are enough subjects in each subgroup (at least 5% of total randomized subjects). In addition, the Gail-Simon test is specified to assess interactions if found to be significant.
5.3 Competing Risk Analysis	The occurrence of symptomatic lower extremity distal DVT event is included in the primary efficacy composite endpoint for the analysis.
5.4 Key Secondary Endpoints	The occurrence of symptomatic lower extremity distal DVT event is included in the key secondary efficacy composite endpoint of symptomatic VTE events and VTE-related deaths
5.4.2 Analysis Methods	Additional supportive analysis of the key secondary endpoints based on the post-randomization observation period is included.
5.6 Additional Secondary Efficacy Endpoints	Definition of an ATE event is clarified. The occurrence of symptomatic lower extremity distal DVT event is included in the additional efficacy composite endpoint 1. Additional composite endpoint of symptomatic events and major bleeding events added.
5.6.1 Definition	The time to first occurrence of fatal/non-fatal ATE is defined. Additional composite endpoint of symptomatic events and major bleeding event is added.
6.1.1 Bleeding Events Classification	Imputation rules for partial bleeding start dates is added.
Changes from v1.0 to v2.0	
1.2.1 Study Drug Discontinuation and Early Withdrawal from Double-Blind Period	Section added describing the details as per the protocol with regards to subject permanently discontinuing study drug.
2.3.1 Intent-to-Treat (ITT) Population 2.3.3 Per-Protocol (PP) Population	Section numbering corrected.
2.3.3 Safety Population	Section added with the definition of safety population.
2.4 Definition of Study Dates and Observation Period End Dates	Definitions of study dates and observation period end dates is further clarified.
2.5 Observation Periods	Table describing the efficacy and safety endpoints and analysis added.
2.5.1 Up-to-Day 180 Observation Period	Section renumbered to be 2.5.1. Censoring rule for subjects who did not experience an event during this observation period updated to be defined as censored at the last day of their complete assessment for study outcomes.
2.5.2 On-Treatment Observation Period	Imputation rule using a conservative approach for randomized subjects but never dosed is added.
2.5.3 Post-Randomization	Censoring rule for subjects who did not experience an event during this observation period updated to be defined as censored at the last contact date is clarified.
2.5.4 Post-First Dose Observation Period	Imputation rule using a conservative approach for randomized subjects but never dosed is added.
2.6 Definition of Subgroups	Tumor type subgroup is clarified.
4.3 Treatment Compliance	Imputation rule in the event of missing information on the returned number of tables added.
4.6 Study Discontinuation and Early Withdrawal from Double-Blind Period	Section updated to include two scenarios with regards to discontinuation from study treatment and withdrawal from double-blind period.

5.1.2 Data Handling Rules	Imputation rule for partial dates is added.
5.2.2 Analysis Methods	The primary composite endpoint analysis will be based on the Up-to-Day 180 observation period for the ITT population
5.2.2.1 Assessment of Proportional Hazards Assumption	In event of non-proportional hazards, alternative approaches were included.
5.2.3 Supportive Analyses for Primary Efficacy Composite Endpoint	Section updated to include supportive analysis based on the on-treatment observation period.
5.2.5.1 Additional Primary Efficacy Composite Endpoint – Include Distal DVT	Additional composite efficacy endpoint defined to include the occurrences of symptomatic lower extremity distal DVT and asymptomatic lower extremity distal DVT.
5.2.5.2 Sensitivity Analysis for Primary Efficacy Endpoint	Clarification for analysis is added.
5.3 Competing Risk Analysis	Section moved from 5.6.
5.4.2 Analysis Methods	Analysis of key secondary efficacy endpoints will be based on the up-to-day 180 observation period.
6.1.3 Supportive Analysis of the Primary Safety Endpoint of Bleeding	Additional supportive analysis of time to multiple bleeding event using recurrent event analysis is added.
Attachments	Illustrations with examples depicting the different observation periods including occurrences of events and censoring rules is added

ABBREVIATIONS

AE	adverse event
ATE	arterial thrombosis event
AESI	adverse event of special interest
APC	advanced pancreatic cancer
CEC	Clinical Endpoint Committee
CI	confidence interval
CMH	Cochran-Mantel-Haenszel
eCRF	electronic case report form
CSR	Clinical Study Report
CU	compression ultrasonography
DPS	Data Presentation Specification
DVT	deep vein thrombosis
ECOG	European Cooperative Oncology Group
EODB	end-of-double-blind period
EOS	end-of-study
EOT	end-of-treatment
HR	Hazard ratio
IDMC	Independent Data Monitoring Committee
ISTH	International Society on Thrombosis & Haemostasis
ITT	Intent-to-treat
MedDRA	Medical Dictionary for Regulatory Activities
PD	pharmacodynamic
PE	pulmonary embolism
PK	pharmacokinetic(s)
PP	per-protocol
RRR	relative risk reduction
SAE	serious adverse event
SAP	Statistical Analysis Plan
SD	standard deviation
T&E	Time and Events
TEAE	treatment-emergent adverse event
VTE	venous thromboembolism

1. INTRODUCTION

This statistical analysis plan (SAP) specifies definitions of analysis populations, derived variables, and statistical methods for analysis of efficacy and safety for the Phase 3b study BAY59-7939/JNJ39039039STM4001. This SAP is based on the Clinical Protocol BAY59-7939/JNJ39039039STM4001 Amendment INT-4 finalized on February 16, 2018.

Titles, mock-ups and programming instructions for all statistical outputs (tables, figures, and listings) will be provided in a separate document entitled Data Presentation Specifications (DPS). This study SAP will be finalized prior to database lock.

This study SAP is also used for the Independent Data Monitoring Committee (IDMC) pre-specified safety reviews. For the IDMC however the definitions and imputation rules are defined based on the data cutoffs and accumulating data at the time of each DMC meetings.

1.1. Study Objectives

Primary Objective

The primary efficacy objective is to demonstrate that rivaroxaban is superior to placebo for reducing the risk of the primary composite outcome as defined by objectively confirmed symptomatic lower extremity proximal DVT, asymptomatic lower extremity proximal DVT, symptomatic lower extremity distal DVT, symptomatic upper extremity DVT, symptomatic non-fatal PE, incidental PE, and VTE-related deaths in ambulatory adult subjects with various cancer types receiving systemic cancer therapy who are at high risk of developing a VTE.

Secondary Objectives

The key secondary efficacy objectives of this study are to compare the efficacy of rivaroxaban with placebo for reducing the risk of symptomatic VTE events and VTE related deaths and all-cause mortality in ambulatory adult subjects with various cancer types receiving systemic cancer therapy who are at high risk of developing a VTE.

Other secondary efficacy objectives include the evaluation of the individual components of the primary efficacy composite outcome variable, confirmed fatal/non-fatal arterial thromboembolism (ATE) events, confirmed fatal/non-fatal visceral VTE events, symptomatic lower extremity distal DVT, a composite of symptomatic lower extremity proximal DVT, asymptomatic lower extremity proximal DVT, symptomatic upper extremity DVT, symptomatic non-fatal PE, incidental PE, and all-cause mortality, and a composite of symptomatic lower extremity proximal DVT, symptomatic lower extremity distal DVT, symptomatic upper extremity DVT, symptomatic non-fatal PE, and VTE-related deaths.

1.2. Study Design

[figure not shown]
This is a multicenter, randomized, double-blind, placebo-controlled, parallel-group, superiority study comparing the efficacy and safety of rivaroxaban with placebo for primary prophylaxis of VTE (defined as DVT and/or PE) in ambulatory adult men and women, 18 years of age and older, with various cancer types who are scheduled to initiate systemic cancer therapy as a component of their standard of care anticancer regimen, who have a baseline Khorana thromboembolic risk score of ≥ 2 , and are judged by the investigator or qualified designee to be an appropriate candidate for treatment with either placebo (10 mg orally once daily for 180 days) or rivaroxaban (10 mg orally once daily for 180 days) for thrombo-prophylaxis based on their clinical status.

The study consists of 3 periods: a 2-week screening period, a 180-day double-blind treatment period with an End-of-Treatment (EOT) visit [for subjects who permanently stop study drug], and a 30-day post-treatment follow-up period with a Day 210/End-of-Study (EOS) visit. The duration of participation in the study for each subject is approximately 32 weeks.

A target of approximately 700 subjects will be randomly assigned into the study in a 1:1 ratio to 1 of 2 treatment groups (rivaroxaban 10 mg qd and placebo) with approximately 350 subjects per treatment group. Towards the end of the enrollment phase, the planned total of subjects to be randomized into the study was revised to approximately 800 subjects due to a higher than originally anticipated subject discontinuation rate. In addition, subjects will be stratified at randomization by tumor type (APC or non-APC) such that approximately 25% of the subjects randomly assigned are those with APC.

Randomized subjects will continue with their recommended systemic cancer therapy (SCT) during the study period and will be examined by compression ultrasonography (CU) at every 8-week intervals. Subjects permanently discontinuing the study drug will be required to have a CU performed within 2 days of receiving their last dose of study drug.

Figure 1: Schematic Overview of the Study

1.2.1. Study Drug Discontinuation and Early Withdrawal from Double-Blind Period

As per the protocol (Section 10.2.2), if a subject permanently discontinued study drug before the Day 180 visit/End of double-blind (EODB) period, this would not result in automatic permanent withdrawal of the subject from the study. Subjects are encouraged to make every effort to continue participation in the study and complete the schedule subsequent study visits until the planned end of their study double-blind duration (Day 180/EODB). All outcomes/events data (VTE, vital status (alive/dead), MI, stroke, and other thrombosis events) and safety data (including bleeding events) are collected. If a subject permanently discontinued study drug prior to Day 180 but continued in the study and completed all study visits up to Day 180, then this subject is considered as having ‘completed the double-blind period’ (that is, participated in the study up to the Day 180 visit).

All subjects including those who discontinued prior to Day 180 visit are contacted by telephone for a Day 210/EOS follow-up assessment. Any outcome/event data (including vital status) reported during this telephone visit is collected at this Day 210/EOS visit as agreed upon by the subject informed consent. In the event a subject withdrew consent or is lost-to-follow up, the vital status data are obtained through public information (death and other registries) per local guidelines and as allowed by local registration.

1.3. Statistical Hypotheses for Study Objectives

The primary hypothesis of this study is that prophylactic treatment with rivaroxaban administered at a dose of 10 mg once daily for up to 6 months will be superior to placebo in reducing the risk of objectively confirmed symptomatic lower extremity proximal DVT, asymptomatic lower extremity proximal DVT, symptomatic lower extremity distal DVT, symptomatic upper extremity DVT, symptomatic non-fatal PE, incidental PE, or VTE-related death in ambulatory adult subjects with various cancer types receiving systemic cancer therapy who are at high risk of developing a VTE.

1.4. Sample Size Justification

This is a 6-month fixed duration study to demonstrate the superiority of rivaroxaban compared with placebo in the ambulatory cancer subjects undergoing systemic cancer therapy. Sample size determination is provided in the protocol Section 11.2 and described below:

Estimates for VTE events in this population vary but point out to a significant benefit (or, reduction in events) over placebo when treated with anticoagulant therapy. Per a recent review of the VTE prophylaxis studies in cancer subjects by Khorana et al (protocol ref 20-22), most RCTs on solid tumors have reported relative risk reductions (RRRs) anywhere between 50% and 64%. The duration of the earlier primary prophylaxis studies was generally between 3 to 4 months, in conjunction with initiation of systemic anticancer therapy. The basis for predictive events is derived from the Vienna CATS group, which utilized the Khorana thromboembolic risk score, and followed 819 ambulatory cancer subjects for symptomatic VTE as an endpoint. In a Kaplan-Meier analysis, the cumulative probability of VTE after 6 months: Khorana thromboembolic risk score ≥ 3 , 17.7% (95% CI: 11.0%-27.8%, N= 93), and 9.6% (95% CI: 6.2%-14.7%, N=221) in

those subjects with a Khorana thromboembolic risk score of 2. Taken together, these results show a symptomatic VTE rate at 180 days of at least 12% in subjects with a Khorana thromboembolic risk score of >2 is reasonable. The adjudication of objectively confirmed asymptomatic DVT and PE is estimated to add an additional 5%-10 % to the primary efficacy composite endpoint.

Based on the above information and recommendations from the Cancer Associated Thrombosis Advisory Council, the sponsor planned the duration of the thromboprophylaxis treatment in the multiple malignancy study up to 6 months. Therefore, our estimates of assumed events rates are relatively conservative given that the period of treatment follow up is longer than earlier RCTs.

In this study with a six-month planned treatment with rivaroxaban, the primary efficacy outcome variable is a composite of any symptomatic DVT, proximal asymptomatic DVT, any PE, and VTE-related death. The study design allows fixed treatment duration of 6 months on each successfully randomized subject. Assuming a cumulative incidence rate of 14.5% for the primary composite events in the placebo group and 6.0% cumulative incidence rate in the rivaroxaban treatment group, a total sample of about 700 randomized subjects (350 per treatment group) will be required to demonstrate approximately 60% relative risk reduction (RRR) in the primary efficacy composite endpoint with a 2-sided Type 1 error rate of 5% and >90% statistical power (calculation performed by EAST 6.3 software) assuming a 20% discontinuation rate. Towards the end of the enrollment phase, approximately 800 subjects were planned to be randomized into the study due to the high subject discontinuation rate. In addition, this sample size will allow for 80% statistical power in each stratum (APC or non-APC) for slightly larger differences in incidence rates between the two randomized treatment groups to be statistically significant.

Essentially, the above overall sample size estimate is calculated based on the following assumptions:

- Effect size: absolute difference in event rates = 8.5%, RRR = 58.6%
 - Primary efficacy composite endpoint event rate in the placebo arm: 14.5%
 - Primary efficacy composite endpoint event rate in the rivaroxaban arm: 6%
- Power: >90%
- Overall α level: 5%, 2-sided
- Probability of dropping out of the study: 20%
- Duration of enrollment period: 12 months
- Duration of study: 6 months (fixed for each randomized subject)

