1.5. Randomization and Blinding

A centralized randomization strategy will be implemented in this study. Subjects will be randomly assigned in a 1:1 ratio to 1 of 2 treatment groups based on a computer-generated subject-randomization schedule prepared by or under the supervision of the sponsor prior to initiation of the study. The randomization will be stratified by tumor type (Advanced Pancreatic Cancer [APC] or non-APC) such that up to approximately 25% of the subjects randomly assigned are those with APC. Using the randomization schedule, the IWRS will assign treatment. The IWRS will also provide the number of the study drug bottle to be dispensed for each randomly assigned subject on Day 1 and at each visit (except Day 180/End-of-Treatment) during the double-blind treatment period. The requestor must use his or her own user identification (ID) and personal identification number (PIN) when contacting the IWRS and will then be asked to provide relevant subject details to uniquely identify the subject. Based on these randomization codes, the study drug will be packaged and labeled in a manner that maintains the double-blinded nature of this study.

The investigator will not be provided with randomization codes. The codes will be maintained within the IWRS, which has the functionality to allow the investigator to break the blind for an individual subject.

Data that may potentially unblind the treatment assignment (ie, events that contribute to the primary and secondary outcome or treatment allocation) will be handled with special care to ensure that the integrity of the blind is maintained and the potential for bias is minimized. This can include making special provisions, such as segregating the data in question from view by the investigators, clinical team, or others as appropriate until the time of database lock and unblinding.

Pancreatic cancer subjects are at a higher risk to develop VTE (VTE Khorana risk score ≥ 2). These subjects are also more likely to discontinue early from the study. Therefore, higher than planned (25%) number of pancreatic subjects were allowed for enrollment into this study.

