5.2.2. Analysis Methods

The primary efficacy composite endpoint analysis will be based on the '**Up-to-Day 180' observation period for the ITT population** with censoring as defined in Section 2.6.

The cumulative distribution function of the time to first occurrence of the primary efficacy composite endpoint will be estimated by the Kaplan-Meier method. The primary statistical hypothesis will be tested using a log-rank test, stratified by tumor type (APC or non-APC).

The estimate of the hazard ratio (HR), RRR (RRR=100*[1-HR] %) and the 95% confidence intervals for the treatment effect will be provided based on a stratified Cox proportional hazard model (stratification factor: APC or non-APC) and including treatment group as a binary covariate (i.e., rivaroxaban, placebo).

The cumulative event rate derived from Kaplan-Meier estimate will also be displayed graphically to evaluate the timing of event occurrence and the consistency of the treatment effect over time.

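### SAP Section 1.4: the stated 80% power in each stratum for slightly larger differences is not supported by the SAP's own overall inputs at the planned 25% APC share

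*SAP*

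**What the plan says.** SAP Section 1.4 plans about 700 randomized subjects, later about 800, and lists its assumptions for the overall estimate: "Effect size: absolute difference in event rates = 8.5%, RRR = 58.6"%; "Primary efficacy composite endpoint event rate in the placebo arm: 14.5"%; 6% on rivaroxaban; "Probability of dropping out of the study: 20"%; overall 2-sided alpha of 5%; power above 90%. It then adds that "this sample size will allow for 80% statistical power in each stratum (APC or non-APC) for slightly larger differences in incidence rates" between the two arms. No stratum rate, stratum size or target difference accompanies that sentence.

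The planned mix is in Section 1.2: "approximately 25% of the subjects randomly assigned are those with APC". Section 1.5 says "Pancreatic cancer subjects are at a higher risk to develop VTE" and "These subjects are also more likely to discontinue early from the study", and records that more pancreatic subjects than the planned 25% were allowed to enrol. It gives neither the new share nor an APC event rate. The planned test is in Section 5.2.2: "The primary statistical hypothesis will be tested using a log-rank test, stratified by tumor type (APC or non-APC").

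**The concern.** A stratum holding a quarter of the subjects has about a quarter of the events. A trial planned with a little over 90% power overall cannot usually keep 80% power in that quarter for an effect only slightly above the overall one, whereas the other three quarters may need no larger effect at all. One sentence describing both strata in the same way therefore looked unlikely to fit either.

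What is at stake is interpretation. APC is the randomization stratum and a listed subgroup (Section 2.7). A reader who trusts the sentence could take a null APC result as informative when the stratum had roughly even odds of detecting the planned difference.

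**Working it through.** **Inputs.** From Section 1.4: placebo 14.5%, rivaroxaban 6.0%, difference 8.5 points, 20% dropout, 2-sided 5%, 6 months fixed follow-up, N=700 or 800. From Section 1.2: 1:1 allocation and 25% APC. My assumptions: the overall 14.5% applies in each stratum; event and dropout times are exponential, so that withdrawn subjects contribute follow-up until censoring.

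**Formulas.** With the 6 months as one time unit, l = -ln(1-p) and m = -ln(1-0.20) = 0.2231.

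- Probability of an observed event: e(p) = l/(l+m) x (1 - exp(-(l+m)))
- HR = ln(1-pT)/ln(1-pC)
- Expected events: D = n per arm x (e(pC) + e(pT))
- Schoenfeld power = Phi(sqrt(D)/2 x |ln HR| - 1.96)

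**The plan's own figure first.** e(14.5%) = 0.1303, e(6%) = 0.0538 and HR = ln(0.94)/ln(0.855) = 0.395. With 350 per arm, D = 350 x 0.1842 = 64.5 and power is 96%. A two-proportion calculation on 280 per arm (350 x 0.80) gives 91%. The stated overall power above 90% reproduces.

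**Strata at 25% APC, placebo 14.5%.**

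| Stratum | N total | n per arm | Power at 8.5 points | Difference for 80% | RRR | Events at that point |
|---|---|---|---|---|---|---|
| APC | 700 | 87.5 | 46% | 11.0 | 76% | 14 |
| APC | 800 | 100 | 51% | 10.6 | 73% | 17 |
| non-APC | 700 | 262.5 | 90% | 7.6 | 53% | 50 |
| non-APC | 800 | 300 | 93% | 7.2 | 50% | 59 |

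The APC requirement is 11.0/8.5 = 1.30 or 10.6/8.5 = 1.25 times the planned difference.

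**Simulation check.** With only 14-17 events the formula is optimistic. Simulated two-sample log-rank tests under the same model (8,000 to 10,000 runs per point) give:

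- APC, 88 per arm: about 42-43% power at 8.5 points, 70-71% at 11.0, 78-79% at 11.7 and 81% at 11.9.
- APC, 100 per arm: 46-47% at 8.5 points, 72% at 10.6 and 80% at about 11.3.
- Non-APC: 81% at 7.9 points (262 per arm) and 80% at 7.4 points (300 per arm).

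So APC needs about 11.3-11.9 points. At 11.9 points the RRR is 11.9/14.5 = 82%.

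**Other formulas.** A two-proportion calculation that discards dropouts puts APC at 12.2-12.8 points, and the Freedman formula gives up to 13.2. Non-APC stays between 6.9 and 8.4 points in every variant tried, always below 8.5.

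**Sensitivity to the unstated inputs** (N=800, Schoenfeld, 20% dropout; shares and APC rates are assumed). In the first two rows both strata keep 14.5%. In the others the non-APC rate is (14.5 - share x APC rate)/(1 - share), so that the overall rate stays 14.5%.

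| APC share | APC rate | non-APC rate | APC needs | non-APC needs |
|---|---|---|---|---|
| 30% | 14.5% | 14.5% | 10.1 (RRR 69%) | 7.4 |
| 40% | 14.5% | 14.5% | 9.2 (RRR 63%) | below 8.5 |
| 25% | 20% | 12.7% | 13.1 (RRR 66%) | 6.7 (RRR 53%) |
| 33% | 16% | 13.8% | 10.4 (RRR 65%) | 7.4 (RRR 53%) |
| 33% | 20% | 11.8% | 11.9 (RRR 59%) | 6.7 (RRR 57%) |
| 33% | 25% | 9.3% | 13.4 (RRR 54%) | 5.8 (RRR 62%) |

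If APC dropout is 30% in the 33%/20% case (non-APC 15.1%, so that 20% holds overall), APC needs 12.2 points (RRR 61%).

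**The case against.** The strongest reply is that nothing numerical is contradicted. The sentence already concedes that more than 8.5 points is needed, and it does not say how much more, so a reader could accept 2.1-2.5 extra points as slight. This stands in part: the sentence is not shown to be arithmetically false, and nobody should infer that it is. Two things still count against it. Section 1.4 itself reports RRRs of 50% to 64% in most earlier solid-tumour trials, and at the planned share APC needs at least 73%. At an RRR of 64% (9.3 points) APC power is only 56-62%. And for non-APC the claim fails in direction however the adverb is read, because that stratum needs less than 8.5 points.

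A second reply is that 14.5% is an overall rate and Section 1.5 describes APC as higher risk and over-enrolled. This also stands as a limit. At the planned 25% share a higher rate only raises the absolute difference needed. With a larger share as well, the two pull against each other: 33% APC at 16% needs 10.4 points, slightly below the base case, and 33% at 20% needs 11.9. In the latter case the required RRRs of 59% and 57% sit close to the planned 58.6%, so the sentence may be defensible on the relative scale. It is, however, worded in incidence differences.

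The protocol section cited in Section 1.4 may hold stratum inputs. Their absence from the SAP is not the complaint.

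**Conclusion.** The per-stratum power statement is not supported by the SAP's own overall inputs at the planned APC share. APC needs about 10.6-11.0 points by formula and about 11.3-11.9 by simulation, against 8.5 planned, and has about 42-51% power at 8.5. Non-APC needs about 7.2-7.9 points, which is no larger difference, and that error is harmless.

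This rests on carrying 14.5% into APC, a 25% share and exponential events and dropout. A reader might infer that APC is underpowered whatever its true rate and share, or that the gap must widen because both exceed plan. The documents do not support either, since they give neither value and the net direction depends on their size.

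Nor does the point reach the main inference. The overall power reproduces, the primary test pools the strata, the hierarchy in Section 5.5 contains no stratum test, and Section 5.2.4 treats the stratum as a subgroup with an interaction test. It is a minor correction of a stated power property.

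**What to change.** Either delete the per-stratum power sentence, or replace it with the detectable difference in each stratum. A possible form: *With [x]% APC among about 800 subjects, placebo rates of [a]% in APC and [b]% in non-APC (weighted average 14.5%), and dropout of [c]% and [d]%, a 2-sided 5% log-rank test has 80% power for [e] points (RRR [f]%) in APC and [g] points (RRR [h]%) in non-APC.*

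The sponsor should enter its own APC share, stratum rates and dropout. If the APC rate is set above 14.5%, the non-APC rate must be set below it. The results should be confirmed by log-rank simulation, because the formula is optimistic with so few events. For that reason the scenario figures above should not be copied in: at 11.9 and 6.7 points (33% APC, rates 20% and 11.8%), a simulation with 4,000 runs gave only about 75% and 77% power.

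The cost is SAP wording and a short simulation. No subjects are added, and the primary analysis, overall power and testing hierarchy do not change. On the absolute scale the statement for APC is likely to read less favourably.
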